7.6 Safety Monitoring

The DSMB will perform the following activities for the study: monitor participant

safety; assess study progress (including participant confidentiality, recruitment, and retention); and, monitor data quality and management. The DSMB members are not recent or active collaborators with any of the project investigators.

8. INTERVENTION DISCONTINUATION

HP extract will be delivered as a single dose; therefore, discontinuation of dosing is not relevant. All side effects and/or adverse events that occur following the single dosing will be recorded and tracked in order to identify a pattern of response that could have an impact on continued study enrollment.

9. STATISTICAL CONSIDERATIONS

9.1 General Design Issues

The primary objective of the PK Study is to determine bioavailability and pharmacokinetic properties of product markers after oral consumption of a daily dose of *H. procumbens* (i.e., capsules containing a total amount of extract yielding 100mg harpagoside) in patients with knee, hip, or hand osteoarthritis. We hypothesize that the pharmacokinetic properties of the *H. procumbens* aqueous-ethanolic extract as described in US Patent 6,280,737 B1 (Appendix 1, example 2), will resemble the results obtained with healthy subjects without osteoarthritis, as reported by Loew et al.¹

Secondary Objective: Compare the bioavailability and pharmacokinetic properties after dosing with an enteric coated capsule to changes found after dosing with a non-enteric coated capsule. We hypothesize the C_{max} , t_{max} , and AUC values for product markers will be enhanced by the cellulose (enteric) coating.

Outcome measures: For each of the study product markers we will examine measures reflecting the pharmacokinetic properties of the HP extract. Specifically, we will measure and evaluate C_{max} , t_{max} , and AUC values.

The study will be conducted using a double-blind randomized control study design. Participants will be randomly assigned at the PK testing session to receive either enteric coated or non-enteric coated capsules containing HP extract.

9.2 Sample Size and Randomization

Sample size is based upon previous research published by Loew and colleagues¹ in which six healthy adult males received a single 150mg harpagoside dose through consumption of 600mg *Harpagophytum* extract HF 8858. The C_{max} value was reached within 1.3 hours following dosing and was calculated as 32.2 ng/mL; the half-life of this dose level was 5.6 hours. Given our plan to compare pharmacokinetic parameters between participants who are dosed with enteric versus non-enteric coated capsules, we doubled the sample size used by Loew and colleagues in order to do this comparison. We will collect complete data from 12 participants.

Treatment Assignment Procedures

Group assignment will be linked to the participant identification (PID) number that will be assigned at the start of the PK Testing Session. Study staff responsible for the PK Testing Session will be given the appropriate PID number to use for the participant attending the Testing Session; the PID number will not indicate specifics of the study product assigned to the individual.

All study staff who have direct contact with study participants and/or are involved in data collection or analysis, including the PI and the study biostatistician, will be blinded as to randomization assignment into study group (i.e., enteric or non-enteric capsules). Knowledge of random assignment will remain blinded until all preliminary data reviews and quality checks are completed.

The randomization procedures and assignment list will be the responsibility of [name], DSMB member. She will have no direct involvement with the study participants, data collection, or statistical analysis of the study data.

Study capsules (i.e., enteric and non-enteric capsules containing HP extract) will be labeled with a product code number; [name] will develop the master list that links the product code number to the specifics of the capsule material. She will send this list to the University of Missouri Healthcare Inpatient Pharmacy which is responsible for preparing the study material. [name] will also generate a list that identifies the product code associated with each participant study code (PID) number; this product/participant study code match will be based on the randomization list. Study staff who prepare the dosing of product to be given to each participant will only know the match of participant study identification code and product code numbers and will not know the study product capsule type (i.e., enteric or non-enteric). Study staff who are working directly with study participants and study data will only know the participant study identification code for an individual. [name] will be authorized to break the blinding process as needed to evaluate SAE and/or Unanticipated Problems.

9.3 Definition of Populations

The PK Study will continue until complete data over the 24-hour period following dosing are collected from 12 participants. Analyses will be conducted on the data collected from these participants. Comparisons between values obtained from participants who received the dose of HP extract in the enteric coated capsules versus data from those who received HP extract in non-enteric coated capsules (6 in each group) will be compared.

9.4 Interim Analyses and Stopping Rules

No interim analyses are planned for the PK Study.

Monitoring of AE, SAE, and Unanticipated Problems will be conducted as described in Section 7. It is possible that enrollment in the study will be suspended based on a review of safety findings. Findings that might trigger a safety review include: the occurrence of SAE; AE or increased frequency of unexpected events.

9.5 Outcomes

9.5.1 Primary Outcomes

Blood samples will be collected on the time schedule listed in sections 6.2.2 and 6.2.5 above. These samples will be assayed in order to determine the following PK parameters for the study product markers.

C_{\max} (ng/mL) – first maximal concentration,

t_{\max} (h) – time to reach the C_{\max} ,

AUC (0-t) (ng/mL) – Area under the curve, and

Terminal $t_{1/2}$ (h) – terminal half-life.

Measures of the study product markers obtained from the random urine collections will also be examined and compared to the pattern of change seen from the serum samples.

9.5.2 Secondary Outcomes

There are no secondary outcomes in the PK Study.

9.6 Data Analyses

Statistical analyses will be conducted to address the study objective to determine bioavailability and pharmacokinetic properties of product markers after oral consumption of a daily dose of HP extract. The analyses will follow the statistical method used by Loew and colleagues.¹

The maximal concentration (C_{\max}) and the time to reach C_{\max} (t_{\max}) will be computed for each study product marker using the assay values obtained from the repeated serum collections. The area under the curve (AUC) will be calculated using the trapezoidal rule. The terminal half-life ($t_{1/2}$) will be calculated using linear regression from the log-linear slope of at least three concentrations.

In order to test the hypothesis that these values will be enhanced for those who received the HP extract in the enteric coated capsules, the outcome measures for the two groups will be compared.

Analyses of the primary outcome measures (C_{\max} , t_{\max} , AUC, and $t_{1/2}$) will be conducted on the timed interval blood samples collected from 12 participants who complete the study protocol. Missing data, therefore, should not be a significant issue, resulting only from cases of an accident or assay problem with a specific sample. If there is a missing value for a specific timed interval sample for an individual, the missing value will be replaced in one of two ways in order to compute the primary outcome measures. (1) The missing value will be replaced with the average of the surrounding values if the missing value is a sample other than the first or last timed interval sample. (2) The missing value will be replaced with the immediately adjacent value if it is either the first timed sample or the last timed sample.

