6.2.2 Enrollment, PK testing, and/or Randomization

Enrollment

Participants who are judged to be eligible to participate by the study physician following all screening procedures will be contacted and scheduled for the PK testing session. At the testing session, participants will be assigned a participant identification number (PID). This PID is linked to their blinded randomization assignment, and linked to their SID.

PK Testing

During the PK testing session (Visit 1) the following assessments will be obtained.

- Current medication use – Participants will provide a listing of any and all medications (prescription and over-the-counter) they have taken since the Screening Session. Anyone who reports using any product listed in Section 4.2 Exclusion Criteria will have the PK testing session rescheduled to allow for a 7-day washout period during which they do not take any of the restricted medications.
- Vital signs – The following vital signs will be recorded as baseline values: heart rate, blood pressure, respiration rate.
- Study product markers – Blood samples will be obtained in order to assess product markers at timed intervals during the 10-hour testing session. Using an indwelling catheter that is inserted in the arm, two samples of blood will be collected at the following intervals following dosing: 0hr, 1 hr, 2 hr, 3 hr, 4 hr, 5 hr, 6 hr, 8 hr, 10 hr. This data collection timing schedule is based on previous research.¹

An exploratory examination of the presence of study product markers in urine will be conducted by collecting random urine samples that are timed, to the extent possible, to blood collection time points. Examination of study product markers in urine is exploratory, and will be conducted with the goal of further informing our understanding of the PK parameters obtained from blood samples. Samples for the measurement of study product markers will be analyzed under the supervision of [name].

- Side effects – Study staff will record occurrence of any side effects during the PK testing session.
- Adverse Events – Any occurrence of an adverse event noted by study staff or reported by a participant will be recorded and categorized by system.

Following all testing session assessments, the appointment time for the follow-up session will be confirmed and the participant will be paid for the testing session.

Randomization

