6.2.4 Follow-up Evaluations

24 hr Evaluation

The following measurements and procedures will be completed at the 24-hour follow-up session.

Visit 2 (24 hours following dosing during the PK Testing Session):

- Vital signs – The following vital signs will be recorded: heart rate, blood pressure, respiration rate.
- Electrocardiogram (ECG) – Standard 12-lead ECGs will be performed at the 24-hour follow-up session. A study physician will review the recording and interpret the findings.
- Laboratory values (CBC, BMP, LFT) – Blood samples will be obtained and CBC, BMP, and LFT assays will be assayed. [name] will review and interpret the lab results.
- Study product markers – Blood and urine samples will be obtained in order to assess level of product markers.
- Side effects – Study staff will record any side effects reported by the participant.
- Adverse Events – Any occurrence of an adverse event reported by a participant will be recorded and categorized by system (i.e., cardiovascular, dermatologic, endocrine/metabolic, gastrointestinal, hematologic, hepatic, musculoskeletal, neurologic, renal, reproductive, or respiratory).

36 hr Follow-up. A phone contact will be made at 36 hours following the dosing time at the PK testing session (i.e., 24 hours following the end of the testing session). During this contact, information regarding any side effects or adverse events that were experienced since the last study visit will be collected.

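### Section 9.6 fills a lost 24 h sample with the 10 h value: AUC(0-24) for harpagoside rises about 22%, and half-life 2.9 to 12.7 times if the filled point enters the slope

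*Protocol*

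**What the plan says.** Protocol section 9.6 expects few missing samples, "resulting only from cases of an accident or assay problem with a specific sample". For those that occur, "the missing value will be replaced in one of two ways in order to compute the primary outcome measures". An interior sample takes the mean of its neighbours. For the two ends of the schedule the rule is: "The missing value will be replaced with the immediately adjacent value if it is either the first timed sample or the last timed sample".

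The same section computes AUC by the trapezoidal rule and terminal half-life by "linear regression from the log-linear slope of at least three concentrations". It does not fix which concentrations those are. Section 9.5.1 lists C_max, t_max, AUC(0-t) and terminal half-life as primary outcomes.

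Section 6.2.2 places the testing-session samples at "0hr, 1 hr, 2 hr, 3 hr, 4 hr, 5 hr, 6 hr, 8 hr, 10 hr", with two blood samples at each time. Section 6.2.4 adds the 24 h visit: "Blood and urine samples will be obtained in order to assess level of product markers", without a number of samples. Section 9.3 continues the study until 12 participants, 6 per arm, have complete 24-hour data.

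**The concern.** The neighbour of the 24 h sample is the 10 h sample, 14 h earlier. For a constituent that is being eliminated, copying that value forward draws a plateau where the curve should be falling. The fill is made expressly to compute the primary outcomes, and nothing in section 9.6 exempts AUC or half-life from it.

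Both measures serve the primary objective, which compares the results with published healthy-volunteer values (section 9.1). AUC is also named in the enteric versus non-enteric hypothesis (section 1.2). With 6 participants per arm, one distorted value is visible in the arm summary.

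**Working it through.** The plan states no figure for the effect of this rule, so there is none to reproduce.

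**Inputs from the protocol.** Sampling times are 0, 1, 2, 3, 4, 5, 6, 8, 10 and 24 h (sections 6.2.2 and 6.2.4). Section 9.2 cites a harpagoside half-life of 5.6 h, t_max 1.3 h and C_max 32.2 ng/mL. Each arm has 6 participants (section 9.3).

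**Assumed.** A one-compartment curve with first-order absorption, for the AUC figures only. The percentages do not depend on C_max or dose.

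**Half-life, if the filled point is used in the regression.** Let ln C = a − k·t over the terminal points. Giving the 24 h point the 10 h concentration is the same as replacing t = 24 by t′ = 10 on the response side. The fitted slope becomes −k·b, where b is the least-squares slope of t′ on t. The half-life is multiplied by 1/b, which depends on the sampling times alone.

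| Terminal points | b | Factor 1/b | 5.6 h reads as |
|---|---|---|---|
| 3 (from 8 h) | 12/152 = 0.079 | 12.67 | 70.9 h |
| 4 (from 6 h) | 32/200 = 0.160 | 6.25 | 35.0 h |
| 5 (from 5 h) | 51.6/239.2 = 0.216 | 4.64 | 26.0 h |
| 6 (from 4 h) | 72.5/275.5 = 0.263 | 3.80 | 21.3 h |
| 7 (from 3 h) | 95.7/311.7 = 0.307 | 3.26 | 18.2 h |
| 8 (from 2 h) | 122/349.5 = 0.349 | 2.86 | 16.0 h |

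With one such participant among six whose true half-life is 5.6 h, the arithmetic arm mean is 5.6 × (5 + factor)/6. That gives 16.5 h with 3 points and 7.3 h with 8. A geometric mean, 5.6 × factor^(1/6), gives 8.55 h and 6.67 h.

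**AUC(0-24), whichever points are used for the slope.** With k = ln 2/5.6 and k_a = 2.41/h (solved from t_max 1.3 h), the curve gives C(10 h) = 11.56 and C(24 h) = 2.04 ng/mL. The rule puts 11.56 at 24 h. The last trapezoid grows by 14 × (11.56 − 2.04)/2 = 66.6 ng·h/mL. The linear-trapezoid total goes from 300.6 to 367.2, and 66.6/300.6 = +22.2%. One participant in six then moves the arm mean by 22.2/6 = +3.7%.

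Sensitivity at t_max 1.3 h:

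| True half-life (h) | 2 | 3 | 4 | 5.6 | 8 | 12 |
|---|---|---|---|---|---|---|
| AUC error (%) | +9.7 | +16.9 | +20.6 | +22.2 | +20.8 | +17.1 |

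**The replacement, at a true half-life of 5.6 h.** The slope is fitted to the measured 5, 6, 8 and 10 h values, and the 24 h value is predicted from it.

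| t_max | Half-life returned | AUC error, replacement | AUC error, present rule |
|---|---|---|---|
| 1.3 h | 5.6 h | 0.0% | +22% |
| 4 h | 7.9 h | +3.8% | +27% |
| 5 h | 12.4 h | +9.4% | +29% |

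The first row is near-exact by construction, because the curve is noise-free and log-linear by 5 h. With 10% random error on each concentration and t_max 1.3 h, the returned half-life runs from about 4.2 to 8.6 h (5th to 95th percentile).

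**The case against.** The strongest objection is that the rule will seldom act. Section 9.3 requires complete 24-hour data from 12 participants, so someone who misses Visit 2 is replaced by further enrolment and not filled in. This stands, and it removes the likeliest cause of a missing 24 h value. What remains is a sample lost to an accident or a failed assay. Section 9.6 foresees that case and wrote the rule for it. The duplicate samples of section 6.2.2 are specified for 0 to 10 h only.

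Second, an analyst may leave the filled point out of the regression. Section 9.6 asks for at least three concentrations without saying which, the choice of terminal points is commonly left to the analysis plan, and section 10.1 places missing-data decisions before unblinding. So the half-life inflation is conditional. The AUC inflation is not, because the trapezoid needs a 24 h value and the rule supplies the wrong one.

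Third, the between-arm hypothesis in section 1.2 names C_max, t_max and AUC, not half-life. C_max is not materially affected, and the arm mean AUC moves by only about 4%. This also stands. It limits the damage to the formulation comparison, but not to half-life as a primary outcome set against published values.

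**Conclusion.** The rule for a missing last sample is wrong for these outcomes and should be reworded. When it acts, harpagoside AUC(0-24) for that participant is too high by about 22% at the cited half-life and t_max. The excess is 21% to 22% for half-lives of 4 to 8 h and smaller outside that range. If the filled point enters the slope, half-life is too long by a factor of 2.9 to 12.7, depending on the number of terminal points. The half-life factors assume a log-linear decline. The AUC figures also assume a one-compartment curve.

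Three stronger readings are not supported:

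- A reader might infer that every lost 24 h sample inflates half-life by at least 3.8 times. That floor holds only for up to six points, and only if the filled point is used.
- A reader might infer that AUC rises by more than 20% for every marker. The protocol gives no half-life for the other extract constituents, and no error is claimed for eicosanoids.
- A reader might give equal weight to the first-sample rule and to the averaging of interior samples. Copying 1 h to 0 h would add about 5% to AUC on the same curve. It would set t_max to 0 h when 1 h is the observed peak, since C_max is the "first maximal concentration". Both effects vanish if absorption starts after 1 h. These cases are minor and do not carry the point.

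**What to change.** Reword section 9.6 only:

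- Use no substituted value for t_max or for the terminal slope.
- For a missing 24 h sample, estimate half-life from at least three measured post-peak samples ending at 10 h. Predict the 24 h concentration from that slope, and use it in the same linear trapezoid as for the other participants.
- If fewer than three measured post-peak samples exist, or the slope is not negative, report half-life and AUC(0-24) as not estimable for that participant and marker.

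The cost is one paragraph of text, with no extra samples or data. The downside is that under late absorption a slope ending at 10 h is too shallow. AUC is then still high by about 4% (t_max 4 h) or 9% (t_max 5 h), well below the error of the present rule. The change should be made before any marker data are seen.

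### Section 9.6 fills a missing 0 h sample with the 1 h value and a missing 10 h sample with the unweighted mean of 8 h and 24 h, which distorts that participant's AUC and can distort t_max or half-life

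*Protocol*

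**What the plan says.** Protocol section 9.6 fixes two replacement rules for a missing timed sample and says that the filled values are used to compute the primary outcomes.

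- Interior samples (the clause excepts both ends of the series): "The missing value will be replaced with the average of the surrounding values if the missing value is a sample other than the first".
- End samples: "The missing value will be replaced with the immediately adjacent value if it is either the first timed sample or the last timed sample".

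Section 6.2.2 gives the session sampling times as "0hr, 1 hr, 2 hr, 3 hr, 4 hr, 5 hr, 6 hr, 8 hr, 10 hr". Section 6.2.4 adds a visit "24 hours following dosing during the PK Testing Session", at which "Blood and urine samples will be obtained in order to assess level of product markers". Section 9.3 requires that "complete data over the 24-hour period following dosing are collected from 12 participants". Taken together, the series is 0, 1, 2, 3, 4, 5, 6, 8, 10 and 24 h. The first sample is 0 h and the last is 24 h, so 10 h is an interior sample.

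Section 9.5.1 defines C_max as the "first maximal concentration" and t_max as the time at which it is reached. Section 9.6 uses the trapezoidal rule for AUC and a log-linear regression on at least three concentrations for half-life. It makes no exception for the sample at dosing or for unequal spacing.

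**The concern.** The only neighbour of the 0 h sample is the 1 h sample. Section 9.2 cites a reference peak within 1.3 h, so the rule can place a near-peak concentration at the moment of dosing, when none of the oral dose has been absorbed. If 1 h is the participant's highest sample, the copied 0 h value ties with it and comes first, and t_max is then 0 h.

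The neighbours of the 10 h sample are 8 h and 24 h, whose midpoint is (8 + 24)/2 = 16 h. Their unweighted mean is a linear estimate for 16 h entered at 10 h.

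The filled values go straight into the primary outcomes. The 0 h fill acts on AUC and, conditionally, on t_max. The 10 h fill acts on AUC and half-life. On the curve used below, neither changes C_max. With six participants per arm, one filled profile is a sixth of the arm.

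**Working it through.** The protocol states no error figure for this rule, so there is nothing to reproduce first. I applied the rule literally to a model profile.

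**Inputs.** From section 9.2: t_max 1.3 h, C_max 32.2 ng/mL and half-life 5.6 h after 150 mg harpagoside. From section 3: a dose of 100 mg. My assumptions: a one-compartment oral curve, dose proportionality, and a true concentration of zero at 0 h.

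**Curve.** ke = ln 2/5.6 = 0.1238/h. Solving ln(ka/ke)/(ka − ke) = 1.3 gives ka = 2.41/h. The scaled peak is 32.2 × 100/150 = 21.5 ng/mL.

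| Time (h) | 0 | 1 | 2 | 3 | 4 | 5 | 6 | 8 | 10 | 24 |
|---|---|---|---|---|---|---|---|---|---|---|
| ng/mL | 0 | 21.09 | 20.54 | 18.32 | 16.20 | 14.32 | 12.65 | 9.88 | 7.71 | 1.36 |

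For the complete profile, linear AUC(0-24) = 200.4 ng·h/mL, sampled t_max = 1 h, and half-life from 8, 10 and 24 h = 5.60 h. The percentages below do not depend on dose if kinetics are linear.

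**Missing 0 h.** The fill is 21.09 instead of 0. The trapezoid weight of the 0 h value is 0.5 h, so AUC changes by 21.09 × 0.5 = 10.5, and 10.5/200.4 = +5.3%. The first maximum moves to 0 h.

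That shift in t_max is conditional. In this model 1 h is the highest sample only if the true t_max is below about 1.41 h:

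| True t_max (h) | Filled 0 h as % of C_max | t_max after fill | AUC change |
|---|---|---|---|
| 1.3 | 100 | 0 h | +5.3% |
| 1.5 | 98 | unchanged | +5.0% |
| 2 | 86 | unchanged | +4.2% |
| 3 | 68 | unchanged | +2.9% |

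**Missing 10 h.** The fill is (9.88 + 1.36)/2 = 5.62 against 7.71, or −27%. The trapezoid weight is (24 − 8)/2 = 8 h, so AUC changes by (5.62 − 7.71) × 8 = −16.7, and −16.7/200.4 = −8.3%. Half-life from the same three points becomes 6.00 h. For true t_max from 0.75 to 3 h, the fill stays about 27% low and AUC is 8% to 10% low.

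**Alternatives for 10 h.**
- Linear in time: 9.88 + (1.36 − 9.88) × 2/16 = 8.81. AUC is +4.4% and half-life 5.45 h. Under the linear trapezoid this equals omitting the point.
- Log-linear in time: 7.71, with no error in AUC or half-life. This is exact only because the assumed decline is mono-exponential.

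**Other interior times.** The neighbours of 1, 2, 3, 4, 5 and 8 h are equally spaced, so the plain mean already equals linear interpolation by time. Only 6 h is also unequally spaced. Its fill is (14.32 + 9.88)/2 = 12.10 against 12.65, and −0.55 × 1.5/200.4 = −0.4% of AUC. A lost 1 h sample is filled badly for a different reason, the curvature near the peak, and time-weighting would not change that.

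**Arm level.** One affected profile in six moves mean AUC by 5.3/6 = 0.9% (0 h) or 8.3/6 = 1.4% (10 h), and mean half-life by 0.4/6 = 0.07 h (10 h only).

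**Missing 24 h, for context.** The rule carries 7.71 forward in place of 1.36. AUC changes by (7.71 − 1.36) × 7/200.4 = +22%, and half-life becomes about 71 h.

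**The case against.** The strongest reply is that the rule will seldom operate. Section 9.3 continues enrolment until 12 participants have complete 24-hour data, section 6.2.2 draws two blood samples at each session time, and section 9.6 expects gaps only from an accident or a failed assay. Missing-data decisions are also made blind (section 10.1). This stands as a limit on impact. It does not repair the rule, which acts only when a sample is missing.

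Two stronger readings are tempting, and the protocol supports neither.

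- A reader might infer that every lost 0 h sample gives t_max = 0 h. It does so only when 1 h is the highest sample. With a later peak, t_max is unchanged.
- A reader might infer that the rule biases the enteric versus non-enteric comparison. The protocol gives no lag time or dissolution data for the coated capsule. If a 2 h lag is assumed, the 0 h fill is zero and harmless in that arm, so the 0 h error would fall mainly on the non-enteric arm. The 10 h error would appear in both arms (−8.3% without a lag, −10.7% with one). The difference between arms is therefore a possibility resting on an assumption.

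It could also be argued that the last timed sample means the last draw of the 10-hour session. In that case 10 h would take the 8 h value: 9.88 against 7.71, or +28%, with AUC about 8.6% too high. That reading is also wrong, in the other direction.

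A separate analysis plan may exist, but this is a rule that the protocol states, not a detail that it leaves open.

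**Conclusion.** The defect is real and narrow. As written, section 9.6 puts a post-dose concentration at time zero and a value belonging to 16 h at 10 h, and both enter primary outcomes. For the affected participant, AUC is off by +5.3% (0 h) or −8.3% (10 h), half-life reads 6.0 h instead of 5.6 h (10 h), and t_max can become 0 h (0 h, only with an early peak). In an arm of six, one such profile moves mean AUC by about 0.9% or 1.4%.

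These sizes rest on the one-compartment curve, on the cited healthy-volunteer values applying here, and on 0 h being drawn before absorption starts. The schedule labels it time 0, without the word pre-dose. The direction of the 0 h AUC error needs only a positive 1 h value and a true 0 h value of zero. The mistiming of the 10 h fill needs no model. The rule should be corrected because the correction is almost free, not because the trial's conclusions are likely to turn on it.

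**What to change.** Rewrite the replacement paragraph in section 9.6:

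- **0 h, plant-derived markers:** set a missing value to zero. Section 4.2 bars dietary supplements for 7 days before dosing, and 7 × 24/5.6 = 30 of the stated harpagoside half-lives. The protocol gives no half-life for the other plant markers, so for them the zero rests on the supplement restriction.
- **0 h, eicosanoids:** these are listed among the product markers in the Précis and may have a non-zero baseline. Do not copy the 1 h value; treat 0 h as missing.
- **Interior samples:** replace the plain mean with interpolation by actual sampling time, linear before the peak and log-linear on the declining limb.
- **C_max and t_max:** take them from observed samples only.

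The clause for a missing 24 h sample is a separate matter, and the changes above do not remove it. Given its size on the same curve, correct it in the same edit by not filling 24 h. AUC for that participant then stops at 10 h: 200.4 − 14 × (7.71 + 1.36)/2 = about 137 against 200.4 on this curve. The text should therefore say that it is not pooled with 24-hour areas as if it were the same quantity.

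The cost is one paragraph of wording, with no extra samples, visits or participants. It should be settled before unblinding.
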